## 10g Monofilament test: four applications on dorsal side of hallux, proximal to toenail, on both left and right foot

A reference from Canadian Diabetes is used for this purpose, https://www.canadianjournalofdiabetes.com/article/S1499-2671(17)30866-3/fulltext

- 1. Touch patient with monofilament on the forearm to establish that sensation is understood
- 2. Instruct patient to say 'yes' every time stimulus is felt. Answer can be 'yes, less than forearm' or 'yes, same or more as forearm'.
- 3. With patient's eyes closed, apply the monofilament to the dorsal area of the great proximal to the nail bed. Apply monofilament for one second each time, bending the filament. Ask patient where possible to identify and grade the quantity of deficit between them and the 'control' area as per point 2.
- 4. Perform the stimulus a total of 4 times, each time having the patient score the test (if sensation felt)
- 5. Total of 8 applications, and score can be 0 if stimulus not perceived, 0.5 if perceived substantially less than on forearm and score of 1 if perceive same or more as on forearm. Score below 3.5 means DN present, score of 3.5 to 5 means risk of DN within next four years, and score 5.5 or higher means low risk of neuropathy.

#### MANDARIN protocol v1.1 dd 20Apr2023

Figure 1. Application of monofilament on dorsal side of hallux

#### Medipin test: one application on dorsal side of hallux, proximal to toenail, on both left and right foot

1. Break tab to expose point - avoid contact with fingers.

2. Grasp device between thumb and index finger lightly enough to permit slight axial slippage if required - utilize textured surface to facilitate control.

3. Apply to skin at a perpendicular to standardize point pressure for improved test consistency and optimize annular contact to generate a 'centre surround' field of enhanced acuity. Establish a control area in an unaffected region (forearm) with an 'average' stimulation level by making several quick applications around the same locality for about 5-10 seconds. Press firmly but carefully using a repetitive, percussive contact.

Avoid high amplitude or 'stabbing' actions - penetration is checked by the annulus but never assumed 'impossible'. Instruct your patient this "normal" area represents a 'sharp' sensation and that this equates to a score of 5 out of 10 (on a 10cm scale).

4. With patient's eyes closed, apply the Medipin once to the dorsal area of the great proximal to the nail bed. Ask patient where possible to identify and grade the quantity of deficit between them and the 'control' area. Answer can be no sensation, 'dull' sensation, and 'sharp' sensation. Patient will also score the sensation on a 10cm visual analogue scale.

5. To prevent re-use destroy point by compression against a hard surface and/or dispose of in a biohazard container.

Figure 2. Medipin device.

#### 5.4 DEFINITION OF END OF STUDY

For participants the study involves only one clinic visit, and once complete then all study involvement is complete. The study itself therefore ends once the last participant has been seen for the single study visit.

#### 5.5 DISCONTINUATION OR WITHDRAWAL OF PARTICIPANTS

Each participant has the right to withdraw from the study at any time. Since this concerns a single visit study, data already collated as part of the study will be retained if a subject withdraws from the study. Participants do not need to give a reason for study withdrawal and their normal clinical care will not be affected should they decide to discontinue participating in the study.

#### 5.6 SOURCE DATA

Source data will include patient's GP records and the Case Record Form for the results of the neuropathy detection test results. Medipin Ltd will have no access to patient data other than pseudo-anonymised data for the test results.

All documents will be stored safely in confidential conditions. On all study-specific documents, other than the signed consent, the participant will be referred to by the study number.

#### 6 EVALUATION PRODUCT

#### 6.1 DESCRIPTION OF MEDIPIN MEDICAL DEVICE

CE-marked neuropathy test device: Medipin (MHRA No. 1321). Medipin is a single-use precision instrument designed to optimize cutaneous pinprick perception. Medipin's protected point is designed to significantly enhance pinprick acuity to achieve useful stimulation and reduce risk of damaging delicate skin. The protective annulus inhibits depth of penetration and protects against self-inflicted "needle stick" injury.

#### 6.2 DISTRIBUTION & ACCOUNTABILITY

Delivery of kits to the centre will be arranged by Medipin Limited. Records will be retained for kits received and on which dates.

#### 7 SAFETY

7.1 SAFETY DEFINITIONS

#### *Table 5, Description of different adverse event reporting definitions.*

Adverse Event (AE)	Any untoward medical occurrence in a patient or other clinical investigation participant taking part in a trial of a medical device, which does not necessarily have to have a causal relationship with the device under investigation. An AE can therefore be any unfavourable and unintended sign (including an abnormal laboratory finding), symptom or disease temporally associated with the use of the device, whether or not considered related to the device.
Serious Adverse Event	A serious adverse event is any untoward medical occurrence that: 
 
results in death
 
is life-threatening
 
requires inpatient hospitalisation or prolongation of existing hospitalisation
 
results in persistent or significant disability/incapacity
 
consists of a congenital anomaly or birth defect.
 
 Other 'important medical events' may also be considered serious if they jeopardise the participant or require an intervention to prevent one of the above consequences. NOTE: The term "life-threatening" in the definition of "serious" refers to an event in which the participant was at risk of death at the time of the event; it does not refer to an event which hypothetically might have caused death if it were more severe.

#### 7.2 PROCEDURES FOR RECORDING ADVERSE EVENTS

All SAEs need to be reported to the sponsor/host Trust R&D immediately and within no more than 24 hours of the investigator team becoming aware of them.

The only devices to be in contact with the patient is the Medipin device and also the 10g monofilament device. These are both minimally-invasive devices, the patient's skin is not pierced through or damaged in proceedings.

#### 7.3 CAUSALITY

The relationship of each adverse event to the trial must be determined by a medically qualified individual according to the following definitions:

**Related**: The adverse event follows a reasonable temporal sequence from Medipin device application. It cannot reasonably be attributed to any other cause.

**Not Related**: The adverse event is probably produced by the participant's clinical state or by other modes of therapy administered to the participant.

### 8 Statistical consideration and data analysis plan

#### 8.1 GENERAL AND BASELINE CHARACTERISTICS

The numbers of patients entering the study will be recorded, as will be number of any study withdrawals. Adverse events will also be recorded – adverse events are only included if the event occurs during the actual study clinic visit. Any preceding or subsequent events will not be considered an adverse event.

In order to describe the sample and facilitate analysis of objectives, the following characteristics and parameters will be collated, either from the patient or the patients' records (using EMIS patient clinical record system), see also Appendix 1:

- Patient demographics, including age, sex and body mass index
- Pre-existing co-morbidities, including peripheral arterial disease, medical treatment for high blood pressure, and foot/toe malformations.
- Use of diabetes related medication

#### 8.2 SAMPLE SIZE CALCULATION

Since Medipin and monofilament do not assess the same nerve types, a true concordance study cannot be conducted. Hence a sample size is calculated for the prevalence of diabetic neuropathy being present. For the sake of a sample size calculation the assumption is that both tests will detect diabetic neuropathy in a conservative 10% of the sampled population. In the literature a ~20% prevalence of diabetic neuropathy in diabetics is reported but many of these reports are from nearly 30 years ago and therefore a more modest percentage is assumed here. Since it is not expected that the concordance will be high due to the different fibres being tested, calculation of a sample size with sufficient power based on a hypothetical concordance rate is not included here.

Using an online calculator, https://sampsize.sourceforge.net/iface/, with the predetermined criteria of a population of 160,000, 95% confidence interval, and precision of 5%, the required sample size is 139 patients.

Subject to submission of an amendment and appraisal of how patient recruitment into the initial cohort fares, we would like to extend the study to detect 2.5% precision. Again assuming 10% prevalence (which will be reviewed once initial 139 patients have been recruited), 95% confidence interval, and the stricter 2.5% precision, a revised new total of 552 patients will be required.

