#### 1 BACKGROUND AND RATIONALE

Diabetes is a chronic condition that can lead to multiple complications affecting various organs, including of the lower limbs. Initial nerve damage in the patient's foot results in loss of protective sensation, diagnosed as diabetic neuropathy (DN). Due to reduced sensation in the feet, patients may walk on a stone stuck in their shoe or not realise foot skin has been damaged; this can then result in ulceration. Poor healing associated with diabetes – because of vascular damage – can then lead to infection and amputation.

Diabetic foot ulcers are the most common type of foot ulcer and are associated with significant health and cost implications. Whereas costs for foot ulcer care were £300m in 2005-06, this had risen to ~£900m to care diabetes related ulceration and amputation care in 2014–15 (Posnett & Franks 2008; Kerr et al, 2019). In the United States, neuropathy is implicated in up to 80% of >50,000 amputations (Smieja et al, 1999). Large studies conducted in Europe in the mid-90s estimated a prevalence of diabetic neuropathy of circa 25% (Young et al, 1993; Tesfaye et al 1996; Cabezas-Cerrato et al 1998). In a more recent study where 10g monofilament testing was utilised, 11.7% of women with normal fasting glucose, 14.4% of women with impaired fasting glucose (IFG), and 18.3% of women with diabetes had LOPS (Ylitalo et al, 2013). It is imperative to ensure DN is diagnosed early in diabetes patients and that they are educated to look after their feet, thereby minimising the risk of further costly and serious complications.

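### Section 8.2 calls a 10% prevalence conservative, but for a fixed absolute precision it is the optimistic choice: 139 patients give ±5 points only up to a prevalence of about 10%

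*Protocol*

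**What the plan says.** Protocol section 8.2 declines to size the study on concordance, because the two devices test different nerve fibres, and sizes it on the prevalence of neuropathy instead. The input is that "the assumption is that both tests will detect diabetic neuropathy in a conservative 10% of the sampled population". The section acknowledges that "a ~20% prevalence of diabetic neuropathy in diabetics is reported" and explains the lower value by saying that "many of these reports are from nearly 30 years ago and therefore a more modest percentage is assumed here". With a "population of 160,000, 95% confidence interval, and precision of 5%, the required sample size is 139 patients". An extension to 552 patients for 2.5% precision, again at 10%, is optional and needs an amendment. The prevalence is to be reviewed after the first 139 patients. The synopsis repeats 10%, 5%, 139 and 552.

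Section 1 gives the prevalence evidence. Mid-1990s European studies "estimated a prevalence of diabetic neuropathy of circa 25"%, and in a more recent study using the 10g monofilament "18.3% of women with diabetes had LOPS".

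**The concern.** In a sample-size section, *conservative* tells the reader that the assumption errs towards a larger sample. Here it does the opposite. Halving the assumed prevalence from about 20% to 10% cuts the requirement from 246 patients to 139.

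The stated reason for going lower is the age of the reports. That does not cover the 18.3%, which the protocol itself presents as more recent and which was obtained with one of the two devices under study.

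Precision is the only justification offered for either sample size. If the prevalence is near the cited values, the detection rates (the primary outcome) will have wider intervals than section 8.2 and the synopsis lead a reader to expect.

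**Working it through.** **Inputs.** From section 8.2: p = 0.10, 95% confidence (z = 1.96), d = 0.05 or 0.025, population N = 160,000, literature prevalence about 20%. From section 1: 18.3% and about 25%.

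**Formula.** n0 = z² p(1−p)/d². With the finite-population correction, n = n0/(1 + (n0 − 1)/N), rounded up.

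**The plan's own figures.**
- d = 0.05: n0 = 1.96² × 0.10 × 0.90/0.05² = 138.3; corrected 138.2, rounded up to 139.
- d = 0.025: n0 = 553.2; corrected 551.3, rounded up to 552.

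Both reproduce. This also shows that the 5% is absolute. A relative 5% of 10% would mean d = 0.005 and an n0 one hundred times as large, about 13,829.

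**Direction.** p(1−p) is 0.09 at 10%, 0.1495 at 18.3%, 0.16 at 20% and 0.1875 at 25%. It increases up to p = 0.5, so a lower assumed p always gives a smaller n in this range.

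**What the two sizes deliver.** Half-width = 1.96 × √(p(1−p)/n), for one device's rate:

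| Prevalence | n = 139 | n = 552 | n for ±5 | n for ±2.5 |
|---|---|---|---|---|
| 10% | ±4.99 | ±2.50 | 139 | 552 |
| 18.3% | ±6.43 | ±3.23 | 230 | 914 |
| 20% | ±6.65 | ±3.34 | 246 | 978 |
| 25% | ±7.20 | ±3.61 | 288 | 1,145 |

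Half-widths are in percentage points. The required n uses the correction with N = 160,000.

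**Margin.** With n = 139, setting the half-width to 0.05 gives p(1−p) = 139 × 0.0025/1.96² = 0.0905, so p is about 10.1%. Above that the target is missed. Even 11.7%, which section 1 reports for women with normal fasting glucose, gives ±5.3.

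**Check with another interval.** Wilson half-widths are ±6.4 for 25/139, ±6.6 for 28/139 and ±7.1 for 35/139. The result does not depend on the simple normal interval.

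**The case against.** **The figures are conditional on 10% and correct there.** This stands. A reader might infer an arithmetic error, or that neither size can deliver its stated precision. The documents do not support that: the 10% is stated openly each time, and both numbers reproduce.

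**The word may only mean a cautious, low estimate.** The section itself glosses it as a more modest percentage and puts the 20% beside it, so nothing is hidden. A low prevalence is also cautious for the number of positive patients (about 14 of 139). But section 8.2 sizes on absolute precision, and for that purpose the word points the wrong way.

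**The cited rates may not transfer.** This stands in part. The 18.3% is from women only. The 25% comes from mid-1990s studies, and two of the titles in the reference list mention hospital clinic patients. This study recruits through GP practices, excludes lower-limb amputation and current foot ulcer, and uses its own set of cut-offs (Table 6). A reader might infer that the true rate is 18% to 25%; the documents do not show that. Equally, they cite no figure for people with diabetes near 10%, and section 8.2 gives only the age of the reports as its reason.

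**The prevalence will be reviewed.** That can correct the 552, but it comes after the first 139 patients and serves only an optional extension.

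**Two further readings to resist.**
- A reader might take the ±5 as the precision of the comparison between devices. Section 8.2 does not claim this. The primary outcome is each device's rate, reported descriptively, and the paired comparison is secondary (section 8.4). For illustration only, the paired half-width is 1.96 × √(2p(1−p)(1−κ)/n) if both rates equal p. Assuming κ from 0 to 0.3, values not in the documents, n = 139 gives ±5.9 to ±7.1 points at 10% and ±7.9 to ±9.4 at 20%.
- The population of 160,000 is close to the sum of the full practice lists in Table 4 (167,613), not the number of people with diabetes. A reader might think this distorts the sample size. It is immaterial: with no correction at all, 138.3 still rounds up to 139, and 552 becomes 554.

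**Conclusion.** The point holds as a mislabelled and unsupported planning assumption. For absolute precision, 10% is optimistic relative to every prevalence the protocol reports for people with diabetes. If the true rate lies between 18.3% and 25%, the half-width from 139 patients is wider than stated by about 1.4 to 2.2 points (6.4 − 5 to 7.2 − 5). From 552 patients it is wider by about 0.7 to 1.1 points (3.2 − 2.5 to 3.6 − 2.5). These sizes rest on the cited rates applying at least roughly to this cohort, and they concern one device's rate.

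Severity is moderate. The study is descriptive on its primary outcome, no analysis becomes invalid, and the initial sample remains useful. What is wrong is the expectation of precision set by the text.

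**What to change.** In section 8.2:
- Delete the word *conservative*. Present 10% as an assumption below the cited values, together with the 18.3% from section 1.
- Keep n = 139 and state that the 95% half-width for a single device's rate is about ±5 points at 10%, ±6.6 at 20% and ±7.2 at 25%.
- State the same for 552: about ±2.5 points at 10%, rising to ±3.6 at 25%.
- Say that the extension size will be recomputed from the prevalence observed in the first 139 patients. As a guide, ±2.5 points would need 978 patients at 20%.

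Carry the two ranges into the sample-size row of the synopsis.

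**Cost:** wording in two places and a less favourable precision statement. No extra patients are needed in the initial cohort. If the sponsor still wants ±2.5 points at a higher observed prevalence, the optional extension would be larger than 552; otherwise the wider interval can be accepted and stated.

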#### 8.3 PRIMARY OUTCOME STATISTICS

The Medipin result and monofilament result (either dorsal or plantar outcome) will be presented with descriptive statistics to show percentage of patients with LOPS / DN.

Test	DN Absent	DN Present
10g Monofilament test plantar side, five	Score of 9 or 10 (out of 10)	Score of 8 or lower
plantar locations on both left and right		
foot		
10g Monofilament test: four applications	Score of 3.5 or higher (out of 8).	Score of 3 or lower
on dorsal side of hallux, proximal to	Recognising that score 3.5 to 5	
toenail, on both left and right foot	considered elevated risk of DN in	
	original reference article.	
Medipin test: one application on dorsal	Sensation in both feet (either 'dull'	No sensation in one or
side of hallux, proximal to toenail, on	or 'sharp' sensation, and score of	both feet
both left and right foot	above 0 out of 10)	

Table 6, Definition and score cut-offs for different DN tests (based on published papers).

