#### Table 2, Overview of comparison between two neuropathy tests

Test result	Medipin: patient reaction	Medipin: patient reaction absent
	present	
10g monofilament*: patient reaction present	No sign of neuropathy	Only small fibre neuropathy
10g monofilament*: patient reaction absent	Only large fibre neuropathy	Both small and large fibre neuropathy

\*Either dorsal test result or plantar test result, and scored accordingly since sum of multiple applications.

- Evaluation of feasibility that a 10-point/cm visual analogue scale (as instructed by manufacturer) can be applied for Medipin in relation to degree of neuropathy, as opposed to standard yes/no quantification. A three-option scoring system (sharp sensation, dull sensation, absence of sensation) applied earlier with pinprick testing will also be recorded (McNeely et al, 1995).
- Relative performance/concordance achieved with 10g monofilament depending on number of tests and locations included in the assessment. This will be application of the monofilament 4x on the dorsal part of the hallux versus application once on five locations on the plantar side of the foot.

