#### 5.2 STUDY PROCEDURES

After completing informed consent, information on relevant clinical parameters and demographics will be collected. See Table 5 for an overview of the activities conducted at the single research visit. The Medipin assessment is an added investigation, whereas the other activities are all part of a diabetes (foot) review.

Table 5, C	Overview d	of study	activities	for study	participants	at single stud	ly visit.
------------	------------	----------	------------	-----------	--------------	----------------	-----------

Activity (in this order)	Reference for rationale
Diabetes status and history	
Patient demographics	
General quality of life questionnaire (EQ-5D-5L)	Herdman et al, 2011
Michigan Neuropathy Screening Instrument symptom	Moghtaderi et al, 2006
10g Monofilament test plantar side, five plantar	GP notebook online resource
locations on both left and right foot	Gr Hotebook online resource
10g Monofilament test: four applications on dorsal side of hallux, proximal to toenail, on both left and right foot	Canadian Journal Diabetes, 2018
Medipin test: one application on dorsal side of hallux, proximal to toenail, on both left and right foot	Boulton et al, 2008

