#### MANDARIN protocol v1.1 dd 20Apr2023

- Apply the filament to a sensitive area of skin (e.g. the forearm) so that the patient is aware of the sensation they are supposed to feel.
- Test 5 sites\* on both feet:
  - ✔ Plantar surface of the hallux and 3rd toe
  - ✓ 1st, 3rd and 5th metatarsal heads
  - \*If callus is present at any of the sites then test at the nearest non-calloused area.
- · Ask the patient to close their eyes and say 'yes' every time that they feel you touch the skin on the foot
- Place the monofilament at 90° to the skin surface
- Slowly push the monofilament until it has bent ~ 1cm (don't jab)
- Hold the monofilament in this position for 1-2 seconds, then slowly release the pressure until the monofilament is
- straight
  Remove contact from the skin
- If the patient does not respond, repeat the test at the site twice. If there is still no response, record as a negative response
- Maximum score 10. A score of 8 or less indicates neuropathy
- Replace monofilament after 500 uses (approximately 6 monthly frequent testing, yearly infrequent testing)

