## Appendix 1, Case Report Form

Patient Code:

MANDARIN-.....

Researcher completing form: .....

item	outcome	
Patient visit date		
Patient age	Years	
Patient height / weight / BMI	Height (m) Weight (kg) BMI	
Year type II diabetes diagnosed		
Smoking status	Never Ex-smoker Current smoker	
Peripheral Arterial Disease (PAD) recorded in notes	No Yes	
Patient on antihypertensive medication?	No Yes (if yes, which medication?)	
Foot and/or toe malformation recorded in notes	No Yes If yes: - Toes - Foot - Both toes and foot	
Current medication for diabetes	Biguanides (Metformin) Alpha-glucosidase inhibitors (eg acarbose miglitol (Glyset))	
	Dipeptidyl peptidase-4 (DPP-4) inhibitors (eg alogliptin (Nesina), linagliptin (Tradjenta), saxagliptin (Onglyza), sitagliptin (Januvia)	
	Glucagon-like peptide-1 receptor agonists (GLP-1 receptor agonists) (eg dulaglutide (Trulicity), exenatide (Byetta), liraglutide (Saxenda, Victoza) lixisenatide (Adylyxin), semaglutide (Ozempic), tirzepatide (Mounjaro)	
	Meglitinides (eg nateglinide (Starlix), repaglinide (Prandin))	
	Sodium-glucose transporter (SGLT) 2 inhibitors (eg canagliflozin (Invokana), dapagliflozin (Farxiga), empagliflozin (Jardiance), ertugliflozin (Steglatro)	
	Sulfonylureas (eg glimepiride (Amaryl), gliclazide Glipizide, glyburide (Glynase), glyburide-metformin)	

	Thiazolidinediones (eg rosiglitazone, pioglitazone-alogliptin (Oseni))	
	Insulin 
 
rapid- or short-acting insulin.
 
mixed insulin.
 
long-acting insulin.
 
	
Medipin outcome (dorsal, hallux)	Left foot (patient's left foot)	
	
 
Sharp sensation
 
Dull sensation
 
Absent sensation
 
Score if sensation felt (5 being forearm reference score):
 
	
	$\bigcirc 0 & 1 & 2 & 3 & 4 & 5 & 6 & 7 & 8 & 9 & 10 \\ \bigcirc \bigcirc \bigcirc & \bigcirc \bigcirc \bigcirc & \bigcirc \bigcirc \bigcirc & \bigcirc \bigcirc \bigcirc & \bigcirc \bigcirc & \bigcirc \bigcirc & 0 & 0$	
	Right foot 
 
Sharp sensation
 
Dull sensation
 
Absent sensation
 
Score if sensation felt (5 being forearm reference score):
 
	
	$\begin{array}{ c c c c c c c c c c c c c c c c c c c$	
Monofilament 10g (dorsal, hallux)	
 
Left foot (1st application)
 
Present sensation (same or more as forearm)
 
Present sensation (substantially less than forearm)
 
Absent sensation
 
	

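### Medipin and the monofilament are scored under unlike positivity rules, so the McNemar comparison and Table 2's fibre-type labels mix scoring rule with fibre type

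*Protocol*

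**What the plan says.** Table 5 in Section 5.2 lists the "Medipin test: one application on dorsal side of hallux, proximal to toenail, on both left and right foot". Section 5.3 gives no retest for it. In Table 6 (Section 8.3) it counts as DN present on "No sensation in one or" both feet; a dull sensation in both feet is DN absent.

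For the dorsal monofilament, Section 5.3 prescribes four applications per foot, each scored 0, 0.5 or 1 and summed over both feet. Table 6 sets DN absent at "Score of 3.5 or higher (out of 8") and DN present at 3 or lower.

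For the plantar monofilament, Section 5.3 tests five sites per foot and says: "If the patient does not respond, repeat the test at the site twice". DN is present at 8 or less out of 10.

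Table 2 (Section 2.2) names a patient who reacts to the monofilament but not to Medipin "Only small fibre neuropathy", and the reverse pattern as large fibre only. Section 8.4 compares the binary results with kappa and McNemar's test, and foresees regressions to compare variables associated with small and large fibre screening.

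**The concern.** The devices differ in three ways besides the nerve fibre they address:

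- **Chances to respond:** one per foot for Medipin, four per foot for the dorsal monofilament, and up to 5 × 3 = 15 per foot for the plantar test.
- **Combining the feet:** either foot suffices for Medipin, while the monofilament scores are summed over both feet.
- **Reduced sensation:** it costs half a mark on the dorsal monofilament and nothing on Medipin.

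A discordant pair can therefore arise from the rule alone. Table 2 leaves no room for that, because each discordant cell is given a fibre diagnosis. Section 1 makes small against large fibre damage the reason for the study, so a significant McNemar result would probably be read as Medipin finding small fibre disease.

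**Working it through.** **Inputs.** The rules come from Sections 5.3 and 8.3, and N = 139 from Section 8.2. The documents give no chance of missing a single stimulus, so this is an assumption, *m*, shown over a range.

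**1. The plan's own figure.** Section 8.2 assumes that "both tests will detect diabetic neuropathy in a conservative 10% of the sampled population". Then n = 1.96² × 0.10 × 0.90 / 0.05² = 138.3. With the finite population correction, n / (1 + (n − 1)/160,000) = 138.2, rounded up to 139. The stated size reproduces and this point does not affect it.

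**2. One patient, no assumption about *m*.** Take complete loss in one foot and normal sensation in the other, the same for both devices.

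| Test | Result | Table 6 verdict |
|---|---|---|
| Medipin | absent in one foot | DN present |
| Dorsal monofilament | 0 + 4 = 4 of 8 | DN absent |
| Plantar monofilament | 0 + 5 = 5 of 10 | DN present |

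With the dorsal result, Table 2 labels this patient as small fibre only, although no monofilament application was felt in the affected foot. With the plantar result, the two devices agree.

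**3. Size if misses are equal and independent.** Every stimulus of either device is missed with probability *m*, so there is no device or fibre difference.

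- Medipin positive: 1 − (1 − m)².
- Dorsal positive: at least 5 of 8 missed, felt applications scoring 1.
- Plantar positive: a site fails with probability m³, and at least 2 of 10 sites fail.
- Exact McNemar: practically all discordant pairs lie one way, so p = 2 × 0.5^b. Five pairs give 0.063 and six give 0.031, so at least six are needed. The chance is P(Bin(139, Medipin rate) ≥ 6).

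| m | Medipin positive | Expected of 139 | Dorsal | Plantar | McNemar significant |
|---|---|---|---|---|---|
| 1% | 2.0% | 2.8 | about 0 | about 0 | 6% |
| 2% | 4.0% | 5.5 | about 0 | about 0 | 47% |
| 5% | 9.75% | 13.6 | 0.0015% | below 0.0001% | 99% |

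Half scores change little: at m = 5.13%, with 20% to 40% of applications scored 0.5, the dorsal rate is 0.015% to 0.11%.

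**4. Relaxing independence.** Let the miss rate vary between patients (beta distribution, mean 5%, the same for both devices) with within-patient correlation ρ. Medipin becomes 2m − m² − ρm(1 − m) = 0.0975 − 0.0475ρ; the monofilament rules follow by averaging over the beta distribution.

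| ρ | Medipin | Dorsal | Plantar |
|---|---|---|---|
| 0.3 | 8.3% | 1.9% | 1.8% |
| 0.5 | 7.4% | 3.3% | 3.4% |
| 0.9 | 5.5% | 4.8% | 4.9% |

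In a mixed population (10% affected with miss rates of 50% to 90%, the rest with 1% to 5%), Medipin ranges from 9.3% to 18.7% and either monofilament rule from 3.6% to 10.0%. With independent misses at one common rate, the order reverses slightly above about 0.70 (plantar) or 0.84 (dorsal).

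**5. Effect of matching the rule.** If the first dorsal monofilament application per foot is scored absent in either foot, its rate under step 3 is also 1 − (1 − m)². At m = 5%, discordance is expected equally both ways: 0.0975 × 0.9025 = 8.8%, or 12.2 of 139. The patient in step 2 becomes positive on both devices.

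**The case against.** The primary objective is the detection rate of each test in a pragmatic, real-world setting. Section 8.3 reports it descriptively, and Table 6 bases its cut-offs on published papers. The rule is then part of the test. This stands: a reader might infer that the primary rates are invalid, but the documents do not support that.

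The protocol is also not blind to the issue. It disclaims a true concordance study, notes under Table 2 that the monofilament result sums several applications, adds a dorsal test partly to match Medipin's site, and flags dorsal scores of 3.5 to 5 as elevated risk. But this matches the site and not the rule, and the binary labels and tests remain.

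Several points limit size and direction, and they stand:

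- The miss rate is assumed. At 1% to 2% the effect (2 to 4 points) is below the planned 5% precision.
- Equal miss rates are doubtful: Medipin asks the patient to choose a category and mark a scale, while the plantar test relies on a spontaneous yes.
- Counting dull as DN absent lowers Medipin positives. Uniformly reduced sensation gives 8 × 0.5 = 4 on the dorsal monofilament, also DN absent, so the half mark makes no difference there.

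A reader might therefore also infer that any Medipin excess will be an artefact. The documents do not support that either; they show only that the planned analysis could not tell.

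**Conclusion.** The point holds for the McNemar comparison and for Table 2's fibre-type labels. It does not hold against the as-practised detection rates or the sample size. The one-foot example follows from the protocol's own rules and needs no assumed miss rate, but it applies to the dorsal monofilament only.

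The numerical size is conditional. Under equal and independent misses, the rules alone could give Medipin 2.0% to 9.75% positive against almost none for the monofilament, for m from 1% to 5%. At m = 5% with correlation 0.3 to 0.9, the contrast with the dorsal test falls from 8.3% v 1.9% to 5.5% v 4.8%. It nearly vanishes only when loss is close to all or none.

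**What to change.** 1. Keep the Table 6 cut-offs and rates as the as-practised result.
2. Reword Table 2's discordant cells as *Medipin only positive* and *monofilament only positive*.
3. Pre-specify a supplementary paired comparison, with McNemar's test and the paired difference. Score the first dorsal monofilament application per foot with Medipin's either-foot rule. Use absent as the main threshold. As a secondary threshold use absent or reduced, taking Medipin dull and the form's "Present sensation (substantially less than forearm") as reduced. These two categories are only approximate counterparts, and the plan should say so.
4. State that a difference between the devices will not be read as fibre type if it disappears under matched rules. If it persists, it is supportive only: the stimuli themselves differ, so matching the rule cannot isolate fibre type.

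The case report form already records each dorsal application and each Medipin category by foot, so the cost is some wording and a few derived variables, with no new data or procedure. The downside is slightly more analysis, and the Medipin difference may look smaller.
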